**Outpatient Consultation(s) - Resource Utilization (since last visit)****Outpatient consultation(s) since last visit:**

*Please document for each outpatient consultation since last visit the technical interventions performed and the symptoms treated.*

**Technical Intervention(s) performed****Symptom(s) treated****Adverse Events:**

*If any of the treated symptoms is an Adverse Event, please report this Adverse Event additionally in the unscheduled records section.*

Hospitalization period(s) - Resource Utilization (since last visit)Hospitalization period(s) since last visit:

*Please document for each hospitalization period since last visit the number of hospitalization days, the technical interventions performed and the symptoms treated.*

*Duration*

Technical Intervention(s) performed

Symptom(s) treated

Adverse Events:

If any of the treated symptoms is an Adverse Event, please report this Adverse Event additionally in the unscheduled records section.

Serious Adverse Events:

Each unplanned hospitalization during therapy or within 30 days thereafter is considered to be an SAE and must be reported additionally on an Adverse Event page in the unscheduled records section.

## Annex 2. EQ5D-5L

Under each heading, please tick the ONE box that best describes your health TODAY

### MOBILITY

I have no problems in walking about	
I have slight problems in walking about	
I have moderate problems in walking about	
I have severe problems in walking about	
I am unable to walk about	

### SELF-CARE

I have no problems washing or dressing myself	
I have slight problems washing or dressing myself	
I have moderate problems washing or dressing myself	
I have severe problems washing or dressing myself	
I am unable to wash or dress myself	

### USUAL ACTIVITIES (e.g. work, study, housework, family or leisure activities)

I have no problems doing my usual activities	
I have slight problems doing my usual activities	
I have moderate problems doing my usual activities	
I have severe problems doing my usual activities	
I am unable to do my usual activities	

[figure not shown]
### PAIN / DISCOMFORT

I have no pain or discomfort	
I have slight pain or discomfort	
I have moderate pain or discomfort	
I have severe pain or discomfort	
I have extreme pain or discomfort	

### ANXIETY / DEPRESSION

I am not anxious or depressed	
I am slightly anxious or depressed	
I am moderately anxious or depressed	
I am severely anxious or depressed	
I am extremely anxious or depressed	

- We would like to know how good or bad your health is TODAY.
- This scale is numbered from 0 to 100.
- 100 means the best health you can imagine.  
0 means the worst health you can imagine.
- Mark an X on the scale to indicate how your health is TODAY.
- Now, please write the number you marked on the scale in the box below.

YOUR HEALTH TODAY = The best health  
you can imagineThe worst health  
you can imagine

UK (English) v.2 © 2009 EuroQol Group. EQ-5D™ is a trade mark of the EuroQol Gr

Confidential Information

No use or disclose outside AbbVie is permitted without prior written authorization from AbbVie  
The Netherlands v 1.4 (26 March 2018). Protocol based on AbbVie shell protocol version 3.0 (22 April 2015) Page 61 of 65

**Annex 3. WPAI****Work Productivity and Activity Impairment Questionnaire Hepatitis C, V2.0  
(WPAI: Hepatitis C)**

The following questions ask about the effect of your hepatitis C on your ability to work and perform normal daily activities. *Please fill in the blanks or circle a number, as indicated.*

1) Are you currently in paid employment?  NO  YES  
*If NO, tick "NO" and skip to question 6.*

The next questions refer to the **past seven days**, not including today.

2) During the past seven days, how many hours did you miss from work because of problems associated with your hepatitis C? *Include hours you missed on sick days, times you went in late, left early, etc., because of your hepatitis C. Do not include time you missed to participate in this study.*

HOURS

3) During the past seven days, how many hours did you miss from work because of any other reason, such as annual leave, holidays, time off to participate in this study?

HOURS

[figure not shown]
4) During the past seven days, how many hours did you actually work?

HOURS. *(If "0", skip to question 6.)*

5. During the past seven days, how much did hepatitis C affect your productivity while you were working?

*Think about days you were limited in the amount or kind of work you could do, days you accomplished less than you would like, or days you could not do your work as carefully as usual. If hepatitis C affected your work only a little, choose a low number. Choose a high number if hepatitis C affected your work a great deal.*

[figure not shown]
Consider only how much hepatitis C affected productivity while you were working.

6. During the past seven days, how much did your hepatitis C affect your ability to perform your normal daily activities, excluding your job?

*By normal activities, we mean the usual activities you perform, such as working around the house, shopping, childcare, exercising, studying, etc. Think about times you were limited in the amount or kind of activities you could perform and times you accomplished less than you would like. If hepatitis C affected your activities only a little, choose a low number. Choose a high number if hepatitis C affected your activities a great deal.*

Consider only how much hepatitis C affected your ability to perform your normal daily activities, excluding your job.

WPAI: HepC V2.0 (English - United Kingdom)

Confidential Information

No use or disclose outside AbbVie is permitted without prior written authorization from AbbVie  
The Netherlands v 1.4 (26 March 2018). Protocol based on AbbVie shell protocol version 3.0 (22 April 2015) Page 63 of 65

## Annex 4. Child-Pugh Classification of Severity of Cirrhosis

Parameter	Points Assigned for Observed Findings		
	1	2	3
Total bilirubin, <math>\mu\text{mol/L}</math> (mg/dL)	<34.2 (<2)	34.2 – 51.3 (2 – 3)	>51.3 (>3)
Serum albumin, g/L (g/dL)	>35 (>3.5)	28 – 35 (2.8 – 3.5)	<28 (<2.8)
INR	<1.7	1.7 – 2.3	>2.3
Ascites*	None	Slight	Moderate to severe
Hepatic encephalopathy**	None	Grade 1 or 2 (or suppressed with medication)	Grade 3 or 4 (or refractory)

\* None.

Slight ascites = Ascites detectable only by ultrasound examination.

Moderate ascites = Ascites manifested by moderate symmetrical distension of the abdomen.

Severe ascites = Large or gross ascites with marked abdominal distension.

\*\* Grade 0: normal consciousness, personality, neurological examination, electroencephalogram.

Grade 1: restless, sleep disturbed, irritable/agitated, tremor, impaired handwriting, 5 cps waves.

Grade 2: lethargic, time-disoriented, inappropriate behavior, asterixis, ataxia, slow triphasic waves.

Grade 3: somnolent, stuporous, place-disoriented, hyperactive reflexes, rigidity, slower waves.

Grade 4: unarousable coma, no personality/behavior, decerebrate, slow 2 to 3 cps delta activity

CI	confidence interval
CNI	calcineurin
CP	core population
CPFSU	core population with sufficient follow-up data
CT	computer tomography
DAA	direct-acting antiviral agent
DDI	drug-drug interaction
EC	ethics committee
EDC	electronic data capture
eCRF	electronic case report form
EMA	European Medicines Agency
EoT	end of treatment
EQ-5D-5L	EuroQol 5 dimension 5 level
FDA	Food and Drug Administration
FIB-4	Fibrosis-4 Score/Index
γ-GT	gamma-glutamyltransferase
HCC	hepatocellular carcinoma
HCP	health care provider
Hb	hemoglobin
HbA1c	hemoglobin A1c
HBV	hepatitis B virus
HCV	hepatitis C virus
HDL	high-density lipoprotein

GLOSSARY OF ABBREVIATIONS

HIV	human immunodeficiency virus
HVPG	hepatic venous pressure gradient
ICMJE	International Committee of Medical Journal Editors
IEC/IRB	independent ethics committee/- review board
IgA	Immunoglobulin A
IgG	Immunoglobulin G
IgM	Immunoglobulin M
INN	international non-proprietary name
INR	international normalized ratio
LDL	low-density lipoprotein
LLoD	lower limit of detection
LLoQ	lower limit of quantification
MAH	Marketing Authorization Holder
MedDRA	Medical Dictionary for Regulatory Activities
MRI	magnetic resonance imaging
NCP	non-core population
NS3/NS4A	nonstructural protein 3/nonstructural protein 4A
NS5A	nonstructural protein 5A
NS5B	nonstructural protein 5B
OATP	organic anion-transporting polypeptide
OLT	orthotopic liver transplant
paritaprevir/r	paritaprevir/ritonavir
PCR	polymerase chain reaction
pegIFN	pegylated interferon
PRO	patient reported outcome
PSP	patient support program
PT	preferred term
RBV	ribavirin
RF	rheumatoid factor
RNA	ribonucleic acid
SAE	serious adverse event
SAP	statistical analysis plan
SD	standard deviation

GLOSSARY OF ABBREVIATIONS

SDP	study designated physician
SNP	single nucleotide polymorphism
SOC	system organ class
SP	safety population
SVR	sustained virological response
SVR12	SVR at 12 weeks after EoT
SVR24	SVR at 24 weeks after EoT
TAI	total activity impairment
TP	target population
TWP	total work productivity impairment
VAS	visual analogue scale
WHO	World Health Organization
WPAI	work productivity and activity impairment
WPAI-GH	WPAI as general health measure
WPAI-SHP	WPAI modified for specific health condition

1 Introduction

The interferon-free combination regimen of paritaprevir/r and ombitasvir with or without dasabuvir (ABBVIE REGIMEN) ± ribavirin (RBV) for the treatment of chronic hepatitis C (CHC) has been shown to be safe and effective in randomized controlled clinical trials with strict inclusion and exclusion criteria under well controlled conditions.

The rationale for this observational study is to determine how the efficacy and safety of the ABBVIE REGIMEN as demonstrated in pivotal trials translates into real world everyday clinical settings, which means evaluating its effectiveness. Whereas efficacy can be defined as a measure of the capacity of a treatment to produce the desired effect in a controlled environment, such as in a randomized controlled trial, effectiveness is the extent to which a drug achieves its intended effect in the usual clinical setting. Effectiveness trials typically have limited exclusion criteria and will involve the broader patient populations in routine clinical practice, treated per local label, which might include patients with heterogeneous compliance patterns and patients with significant comorbid conditions and could be used to model and disseminate best practices. Effectiveness research allows for external patient-, provider-, and system-level factors and can therefore be more relevant for health-care decisions by both providers in practice and policy-makers.

This observational study is the first effectiveness research examining the ABBVIE REGIMEN ± RBV, used according to local label, under real world conditions in the Netherlands in a clinical practice patient population.

During the last decade, when dual therapy with pegylated interferon (pegIFN) plus RBV was standard of care for the treatment of CHC, the discovery of predictive factors for virological response and the subsequent development of treatment algorithms marked a milestone in patient care for CHC. As a consequence, treatment could be effectively targeted to patients most likely to respond. Interestingly, many of the now well established predictors of response to pegIFN/RBV and first generation direct acting antivirals (DAAs) in combination with pegIFN/RBV were not predictive of outcome in the development trials of the ABBVIE REGIMEN ± RBV. This observational study may play an important part in bridging the data gaps. It may help identify predictive factors of response that are important in real world treatment settings and thus, could assist in further optimizing treatment with the interferon-free ABBVIE REGIMEN ± RBV in the future.

The label of the ABBVIE REGIMEN ± RBV will vary according to hepatitis C virus (HCV) genotype/subtype and stage of liver disease. It is therefore relevant to understand the pattern of use and outcome in daily clinical practice. In addition, this study will provide data on the impact of adherence on treatment outcomes in everyday settings, which may help treating physicians to improve the management of patients under their care.

The main aim of this observational study is to provide evidence of the effectiveness of the ABBVIE REGIMEN ± RBV in a real world setting across clinical practice patient populations.

2 Study Objectives

The objectives of this study are:

Primary objective:

1. To describe in routine clinical practice the effectiveness of the interferon-free ABBVIE REGIMEN ± RBV in patients with CHC as evidenced by sustained virological response at 12 weeks after end of treatment (SVR12)

Secondary objectives:

2. To describe the pattern of real world use of the ABBVIE REGIMEN ± RBV with respect to different patient and treatment characteristics
3. To evaluate the influence of adherence on treatment outcome in routine clinical practice
4. To describe the tolerability of the ABBVIE REGIMEN ± RBV
5. To document the effect of the ABBVIE REGIMEN ± RBV on PROs and work productivity in the Dutch population
6. To determine the impact of the ABBVIE REGIMEN ± RBV on healthcare resource utilization

3 Study Design

3.1 Overview of Study Design and Dosing Regimen

This is a prospective, multi-center observational study in adult patients chronically infected with HCV receiving the interferon-free ABBVIE REGIMEN ± RBV.

University centers and outpatient clinics qualified by training and experience in the management of patients with CHC participate in this study.

The prescription of a treatment regimen is at the discretion of the physician in accordance with local clinical practice and label, is made independently from this observational study and precedes the decision to offer the patient the opportunity to participate in this study.

After written informed consent has been obtained, patient data including demographic data, HCV disease characteristics, co-morbidities, co-medication, treatment details, and laboratory assessments as recorded in the patient's medical records (source documentation) are documented in the electronic case report form (eCRF). Patients are observed for the duration of the ABBVIE REGIMEN therapy and for up to **24** weeks after treatment completion.

[figure not shown]
The observational period for patients receiving 12 weeks of ABBVIE REGIMEN is max. **36** weeks (12 weeks treatment and **24** weeks post-treatment observation) and for patients receiving 24 weeks of ABBVIE REGIMEN the observational period is max. **48** weeks (24 weeks treatment and **24** weeks post-treatment observation).

Follow-up visits, treatment, procedures and diagnostic methods follow physicians' routine clinical practice. The observational study period entails the following data collection schemes, data documented are those closest to the time windows as indicated in Figure 1:

- 12-week treatment regimen: **four** visits plus two interim data collection windows
- 24-week treatment regimen: **four** visits plus three interim data collection windows

This schedule is based on the anticipated regular follow-up for patients undergoing treatment for CHC.

Figure 1 - Study Flowchart

3.2 Sample Size Calculation

The sample size of the study is not based on statistical considerations. It is expected that 50-55 patients can be enrolled.

4 Statistical Considerations and Analytical Plan

4.1 Primary and Secondary Parameters

4.1.1 Primary Effectiveness Parameter

The percentage of patients achieving SVR12 (HCV RNA <50 IU/mL 12 weeks [i.e. 70 to 126 days] after the last actual dose of the ABBVIE REGIMEN).

Please note, in the study protocol no upper boundary for the time window was specified. The upper boundary of 126 days was introduced to achieve consistency with other studies investigating the ABBVIE REGIMEN ± ribavirin (RBV) for the treatment of CHC. For the handling of missing values see section 4.2.3.

4.1.2 Secondary Parameters

The secondary effectiveness endpoints are:

- The percentage of patients with virological response (HCV RNA <50 IU/mL) at EoT (defined as last intake of ABBVIE REGIMEN or ribavirin)
- The percentage of patients with relapse (defined as HCV RNA <50 IU/mL at EoT followed by HCV RNA ≥50 IU/mL)
- The percentage of patients with breakthrough (defined as at least one documented HCV RNA <50 IU/mL followed by HCV RNA ≥50 IU/mL during treatment).
- Sustained virological response 24 weeks after EoT (SVR24, i.e. patients with HCV RNA < 50 IU/mL 24 weeks after EoT)
- The number and percentage of patients meeting each and any of the following SVR12 non-response categories:
 - On-treatment virologic failure (breakthrough [defined as above] or failure to suppress [each measured on-treatment HCV RNA value ≥50 IU/mL])
 - Relapse (defined as HCV RNA <50 IU/mL at EoT followed by HCV RNA ≥50 IU/mL post-treatment for subjects who complete treatment [not more than 7 days shortened])
 - Premature study drug discontinuation with no on-treatment virologic failure
 - Missing SVR12 data and/or none of the above criteria

Further secondary variables are:

- Type of treatment regimen (± Dasabuvir, ± RBV, intended and actual combination, dose and duration)
- Adherence
 - Percentage of the DAA dose taken in relation to the target dose of DAA (cumulative dose taken divided by target dose in percent)
 - Percentage of the RBV dose taken in relation to the target dose of RBV (cumulative dose taken divided by target dose in percent)
 - Percentage of missed RBV treatment days in relation to the target number of RBV treatment days
- Co-morbidities and concomitant medication
- Serious and non-serious adverse events and pregnancy occurrences

- Questionnaires on PROs: e.g. EuroQol 5 dimension 5 level (EQ-5D-5L) questionnaire and work productivity and activity impairment (WPAI) questionnaire prior to treatment initiation, at EoT as well as **12 and 24** weeks after EoT
- Healthcare resource utilization

No data will be imputed for any effectiveness or safety analyses except for the analyses of the HCV RNA endpoints and PRO questionnaires (if applicable). For further details see sections 4.2.3 and 4.2.7.2.2, respectively.

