4.2.2 Definition of Baseline and Visit Time Windows

This observational study covers three documentation periods, see Figure 1. An overview of data to be collected throughout the study is summarized in Table 1.

Table 1 - Data Documentation Schedule

Assessment/ Procedure (only available data to be collected; no diagnostic or monitoring procedures to be applied to the patients apart from those of routine clinical practice)	Baseline	Treatment Period			Post-treatment (PT) Period		
		On-treatment visits	Mid treatment visit for pts receiving 24 weeks of therapy	EoT ^b	Early PT visit	SVR 12 visit	SVR 24 visit
Informed Consent	X ^a						
Demographic information	X						
IL28B	X						
Relevant CHC disease characteristics	X						
Liver fibrosis stage	X						
CHC treatment history	X						
HCV genotype and subtype	X						
HCV RNA samples	X	X	X	X	X	X	X
Clinical chemistry and hematology	X	X	X	X	X	X	X
ABBVIE REGIMEN initiation documentation	X						
ABBVIE REGIMEN adherence		X	X	X			
Concomitant medication	X	X	X	X			
Relevant medical history, co-morbidities	X						
sAE, AE and pregnancy reporting	X	X	X	X	X ^c	X ^d	X ^d
For patients receiving RBV: Evidence, in accordance with local label, that female patient or female partner of male patient is not pregnant	X						
Patient questionnaires – WPAI, EQ5D-5L	X			X		X	X
Health care resource utilization	X	X	X	X			

Abbreviations: EoT = End of Treatment (at Week 12 or 24 or at premature discontinuation),

PT = Post-Treatment

a Written informed consent must be obtained before any data documentation in the eCRF

b Patients who prematurely discontinue should return to the site to document EoT data

c Tolerability documentation until PT week 4

d Pregnancy reporting for patients treated with DAA +/- RBV

In accordance with the non-interventional nature of the study all HCV RNA measurements will be performed at the sole discretion of the physician and all HCV RNA measurements have to be entered into the eCRF. All recorded HCV RNA values will be assigned to appropriate time points (baseline, on-treatment visits, EoT visit, post-treatment visits) as follows:

Table 2 - Analysis Time Windows for HCV RNA

Phase	Time point	Time Window
Pre-Treatment	Baseline	Last value prior to start of study treatment (i.e. \leq study day 1)
On-treatment		Study day during treatment period ^{^#} (Study day 1 = first treatment day)
Treatment Week	4 (RVR*)	15 - 42 [^]

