EoT	Actual EoT	Study day of last dose# (28 days prior to last dose - 7 days post last dose)
Post Treatment	12 weeks (SVR 12 window)	\geq 70-126 days post last dose
	24 weeks (SVR24 window)	127-210 days post last dose
	48 weeks\$	> 210 days post last dose

[^]values must also be \leq 7 days post last dose

\geq study day 2

*RVR = rapid virological response

\$ Please note that this time window is not specified in the study protocol, but added to consider possible relapse after day 210 in the analysis of the relapse rate. Analyses of SVR48 are not planned.

All reported safety laboratory test results will be assigned to one of the time points using the time windows specified in the table below.

Table 3 - Analysis Time Windows for Safety Laboratory Data

Phase	Time point	Time Window
Pre-Treatment	Baseline	Last value prior to start of study treatment (i.e. \leq study day 1)
Treatment Weeks	4 (day 29)	Study day during treatment period (Study day 1 = first treatment day)
	8 (day 57)	15 – 42 [^]
	12 (day 85)	43 – 70 [^]
	16 (day 113)	71 – 98 [^]
EoT	Actual EoT	Study day of last dose# (28 days prior to last dose - 7 days post last dose)
Post Treatment	4 weeks (28 days post last dose)	8– 56 post last dose
	12 weeks (84 days post last dose)	57 – 126 days post last dose
	24 weeks (168 days post last dose)	127 – 252 days post last dose
	48 weeks (336 days post last dose)\$	253 – 420 days post last dose

[^]values must also be \leq 7 days post last dose

\geq study day 2

\$ Please note that this time window is not specified in the study protocol, but added to consider possible reported values.

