4.2.3 Handling of missing data

No data will be imputed for any effectiveness or safety analyses except for the analyses of the HCV RNA endpoints and certain PRO endpoints. The discussion of missing data imputation for the PRO endpoints is included in section 4.2.7.2.2.

HCV RNA values will be selected for an RVR, EOTR and SVR analysis based on visit windows as defined in Table 2. When there is no HCV RNA value in a visit window based on defined visit windows, the closest values before and after the window, regardless of the value chosen for the subsequent and preceding window, will be used for the flanking imputation described below. For

analysis of RVR, EOT and SVR, if a subject has a missing HCV RNA value at a post-Day 1 visit but with undetectable or unquantifiable (LLoD or LLoQ \leq 50 IU/mL) HCV RNA levels at both the preceding value and succeeding value, the HCV RNA level will be considered undetectable or unquantifiable, respectively, at this visit for this subject. In addition, if a subject has an unquantifiable HCV RNA level at the preceding value and an undetectable HCV RNA level at the succeeding value, or vice versa, the HCV RNA level will be imputed as unquantifiable at this visit for this subject.

For analyses of RVR, subjects still missing a value for the visit after flanking imputation will be considered as a failure. For EoTR and SVR analysis, if there is no value in the appropriate window after flanking imputation but there is an HCV RNA value after the window, then it will be imputed into the EoTR or SVR window respectively. Subsequent to this flanking and backward imputation, if the HCV RNA value remains missing at a specific time point, then the subject will be considered as virological failure at this time point (i.e., not undetectable or unquantifiable).

If a subject starts another treatment for HCV, then all HCV RNA values for this subject measured on or after the start date of the new HCV treatment will be excluded from analyses. The subject will be considered a failure for summaries of viral response at all time points after the start of the new HCV treatment.

Due to the non-interventional nature of this study several different methods for determination of the HCV RNA value can be applied. For the purpose of the statistical analysis, a HCV RNA measurement is considered <50 IU/mL,

- if a PCR test was used

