4.2.6.3 CHC treatment history

For treatment-experienced patients the most recent prior treatment and the outcome to prior treatment as reported by the investigator in the eCRF (Null response, Partial response, Breakthrough, Relapse, Sustained virological response (SVR) followed by reinfection, Discontinued [and none of the above], Unknown/ None of the above) will be summarized in frequency tables. In addition to the frequency of each medication (IFN alpha, PEG IFN-alpha, IFN NOS, PEG IFN NOS, Ribavirin, DAA), the frequency of the combinations (pegIFN alpha + RBV, pegIFN alpha + RBV + Telaprevir, XXX) will be summarized.

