4.2.6.4 Co-morbidities and co-infections

A summary table will present the absolute and relative frequencies of HCV co-infections, CHC related comorbidities and other co-morbidities, in more detail:

- HCV Co-infections
 - Human immunodeficiency virus (HIV)
 - Hepatitis B virus (HBV)
 - Tuberculosis
 - Schistosomiasis
- Liver and/ or CHC related co-morbidities
 - Liver transplantation
 - Hepatocellular carcinoma
 - Steatosis (non-alcoholic)
 - Alcoholic liver disease
 - Primary biliary cirrhosis
 - Auto-immune hepatitis
 - Wilson disease

- Cryoglobulinemia
- Porphyria cutanea tarda (PCT)
- Auto-immune skin disease
- Other co-morbidities
 - Kidney transplant
 - Chronic kidney disease (Mild, Moderate, Severe, Currently on dialysis, Currently not on dialysis)
 - Psychiatric disorders (Depression, Bipolar disorder, Schizophrenia, Personality disorder)
 - Diabetes mellitus (Type 1, Type 2)
 - Insulin resistance
 - Metabolic syndrome
 - Lipid disorder
 - Hyperthyroidism
 - Hypothyroidism
 - Cardiovascular disease (Myocardial infarction, Angina pectoris, Hypertension, Stroke)
 - Immunologically mediated disease
 - Hemophilia
 - Thalassemia
 - Sickle cell anemia
 - V. Willebrand disease
 - Psychoactive substance dependency (Active injection drug use, Inhalate cocaine, Marijuana/ cannabis, Opiate substitution)
 - Other

The patient's alcohol consumption will be displayed in a further table, i.e.:

- Alcohol use (None, Yes – occasional, Yes – regular, Ex-drinker [6 units/drinks per day, none in the last 3 months])
- Average number of units/drinks per week (if regular alcohol use is reported)

One unit/drink is defined as 10 milliliters (or approximately 8 grams) of pure alcohol and equals: 200 ml of beer or 100 ml of wine or 20 ml of hard liquor.

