4.2.7.2 Secondary Variables

4.2.7.2.1 Secondary Effectiveness Variables

Response

For the other response rates (i.e. SVR24, EoT response rate, relapse rate, viral breakthrough), the simple percentage of patients and a two-sided 95% confidence interval (CI) of the percentage will be computed (based on the Wilson's score method) as well. The EoT response rates will be reported for CP and the SVR24 rates will be reported for the respective CPSFU, stratified by genotype and cirrhosis status and overall. The relapse rates will be estimated stratified by SVR window (i.e. during SVR12 window=relapse₁₂, during SVR24 window=relapse₂₄, after SVR24

window=relapse_{late}) and stratified by genotype and cirrhosis status and overall in patients of the CP with EoT response who fulfilled the following criteria:

- completed treatment as defined previously,
- had at least one HCV RNA measurement ≥ 70 days post-treatment or was a treatment failure between EoT and 70 days post-treatment.

Viral breakthrough rates [defined as at least one documented HCV RNA <50 IU/mL followed by HCV RNA ≥ 50 IU/mL during treatment] will be estimated overall and stratified by genotype and cirrhosis status in all patients of the CP, who have at least one undetectable or unquantifiable, on-treatment HCV RNA measurement and at least one on-treatment or EoT measurement thereafter.

Non-Response

In another table, the numbers and the percentages of the SVR12 non-responder categories and responder will be summarized for CP patients, overall and stratified by genotype and cirrhosis status. The following SVR12 non-response categories will be considered:

- On-treatment virologic failure (breakthrough [defined as at least one documented HCV RNA <50 IU/mL followed by HCV RNA ≥ 50 IU/mL during treatment] or failure to suppress [each measured on-treatment HCV RNA value ≥ 50 IU/mL])
- Relapse (defined as HCV RNA <50 IU/mL at EoT followed by HCV RNA ≥ 50 IU/mL post-treatment and completed treatment as defined previously)
- Death and none of the above
- Premature study drug discontinuation with no on-treatment virologic failure and none of the above
- Insufficient virological response, other than those mentioned above (patients for whom insufficient virological response was reported, or who had HCV RNA ≥ 50 IU/mL post EoT) and none of the above
- Missing SVR12 data and/or none of the above criteria

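### The relapse endpoints have no time limit and no reinfection category, so a new infection during follow-up would be reported as relapse, mainly in the 24-week and late rates

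*SAP*

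**What the plan says.** SAP 4.1.2 lists as a secondary endpoint "The percentage of patients with relapse (defined as HCV RNA <50 IU/mL at EoT followed by HCV RNA ≥50 IU/mL". It sets no latest date and no condition on genotype, subtype or sequence. Protocol 9.7.3.2 has the same form.

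SAP 4.2.7.2.1 narrows who is analysed. The relapse rate covers CP patients with EoT response who completed treatment (not shortened by more than 7 days) and who have a value at least 70 days post-treatment or failed earlier. The matching SVR12 non-response category reads "Relapse (defined as HCV RNA <50 IU/mL at EoT followed by HCV RNA ≥ 50 IU/mL post-treatment and completed treatment as defined previously". The other categories in that list are on-treatment failure, death, premature discontinuation, other insufficient response, and missing or none of these. None is reinfection.

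On timing, "The relapse rates will be estimated stratified by SVR window": relapse12, relapse24 and relapse_late. The footnote to SAP Table 2 says that the window beyond day 210 was "added to consider possible relapse after day 210 in the analysis of the relapse rate".

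Reinfection appears once, in SAP 4.2.6.3, among the outcomes of the most recent prior therapy: "Sustained virological response (SVR) followed by reinfection". It stands there as a separate option from relapse. The item "HCV genotype and subtype" is scheduled at baseline only, in both SAP Table 1 and Protocol Table 2.

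**The concern.** Relapse is read as return of the treated virus, and so as failure of the regimen. Reinfection is a new event after the treated virus has been cleared. The plan recognises the difference in a patient's history but not after the study treatment, so the same course of events carries two different names depending on when it happened.

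Re-exposure is foreseeable in this cohort. Protocol 7.1 names injection drug use as the most frequent route of transmission, and SAP 4.2.6.4 includes "Psychoactive substance dependency (Active injection drug use" among the recorded co-morbidities. A patient who is negative in the SVR12 window and positive later is the case in which reinfection is most plausible. That patient enters relapse24 or relapse_late with no qualifier. At stake is the interpretation of a named secondary effectiveness endpoint with a small denominator, where one patient is visible in the result.

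**Working it through.** The documents state no relapse or reinfection figure, so there is nothing to reproduce. The check has three parts.

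**1. Tracing a patient through the rules.** Take a CP patient who completes treatment, has HCV RNA <50 IU/mL at EoT and in days 70 to 126, and acquires a new infection detected on day 180.
- The endpoint definition in SAP 4.1.2 is met: <50 at EoT, then ≥50.
- The inclusion rule in SAP 4.2.7.2.1 is met: completer, EoT response, value at or beyond day 70.
- Day 180 lies in the SVR24 window (127 to 210), so the case counts in relapse24. On day 220 it would count in relapse_late.
- No rule removes or relabels it. The rule on new HCV treatment in SAP 4.2.3 drops only values from the start of retreatment onward.

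The three-way split is by time and not by cause.

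**2. Expected number of events.** Inputs:
- 50 to 55 patients (SAP 3.2).
- 24 weeks of planned follow-up (Protocol 9.2.2), or 30 weeks to the end of the SVR24 window at day 210 (SAP Table 2).
- A reinfection rate of 1 to 5 per 100 person-years. This is an assumption; no document gives one.

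Events = patients × weeks / 52.18 × rate, and the chance of at least one is 1 − exp(−events).

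| Period | Person-years, low | Person-years, high | Events | Chance of ≥1 |
|---|---|---|---|---|
| From EoT | 50 × 24/52.18 = 23.0 | 55 × 30/52.18 = 31.6 | 23.0 × 0.01 = 0.23 to 31.6 × 0.05 = 1.58 | 21% to 79% |
| After week 12 | 50 × 12/52.18 = 11.5 | 55 × 18/52.18 = 19.0 | 11.5 × 0.01 = 0.12 to 19.0 × 0.05 = 0.95 | 11% to 61% |

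The second row is the relevant one for relapse24 and relapse_late.

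**3. Effect of one event on the reported rate.** The interval is the Wilson score, as planned: centre (p + z²/2n)/(1 + z²/n), half-width z√(p(1−p)/n + z²/4n²)/(1 + z²/n), with z = 1.96.
- 0/50: upper limit 3.84/(50 + 3.84) = 7.1%, so 0 to 7.1%.
- 1/50: centre (0.02 + 0.0384)/1.0768 = 5.42%, half-width 5.07%, so 2.0% (0.4 to 10.5%).
- 2/50: 4.0% (1.1 to 13.5%).
- With 55 patients: 0/55 gives 0 to 6.5%, and 1/55 = 1.8% (0.3 to 9.6%).

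These denominators assume that every enrolled patient is an evaluable CP completer with EoT response. The real denominator will be smaller and the shift per case larger. The rates are also broken down by genotype and cirrhosis: in an illustrative stratum of 10, one case gives 10% (1.8 to 40.4%).

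**The case against.** **The late events are already shown apart.** This is partly right. The split into relapse12, relapse24 and relapse_late keeps late viraemia out of the 12-week rate. The late window will also be thin, because observation ends at 24 weeks and SVR48 analyses are not planned. But the cases still carry the name relapse.

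**Counting all viraemia as relapse is conservative and follows the protocol.** This stands as a reason to keep the stated rate as the main analysis. Removing failures on an investigator's undefined judgement could bias the result in the sponsor's favour. Typing is also imperfect: SAP 4.2.1 pools mixed and unknown genotype 1 subtypes with 1a, and in a mixed infection a different later subtype need not be a new virus.

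**The size rests on an assumed rate applied to everyone.** This stands too. The mode-of-infection list in SAP 4.2.6.2 describes how the first infection was acquired, not current exposure, and the cohort's mix is unknown. After week 12 the expected count is below one even at the top of the assumed range.

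**Stronger readings that the documents do not support.** A reader might infer that reinfection leaks into the primary analysis, because when an SVR window is empty, SAP 4.2.3 says "but there is an HCV RNA value after the window, then it will be imputed into the EoTR or SVR window respectively". That route does not change the CP SVR12 rate: under the same section, a value that is still missing after imputation also counts as failure, so the patient fails either way. A reader might also infer that every later positive is called relapse. The analysed rate covers completers only; a non-completer falls into another failure category, also without a reinfection label. Finally, one misclassified patient might seem to match the whole relapse rate implied by Protocol Table 1. That table spans 90% to 100%, and SVR12 non-response is not the same as relapse.

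**Conclusion.** The point holds for the relapse endpoints. As written, any HCV RNA ≥50 IU/mL after EoT response in a CP treatment completer is relapse, however late, and reinfection has no category. A documented reinfection would be reported as failure of the regimen, most likely in relapse24 or relapse_late.

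The effect is modest and uncertain: about 0.2 to 1.6 expected events from EoT, or 0.1 to 0.95 after week 12, with each event worth about 2 percentage points on 50 patients. This rests on the assumed 1 to 5 per 100 person-years applied uniformly to all patients. There may well be no such case, and then no result changes. The case for acting is that the rule is cheap to set before the relapse tables are seen, and hard to defend if it is set afterwards.

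**What to change.** Keep the stated relapse rate as the main analysis and leave the SVR12 and SVR24 rules unchanged. Then:

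- Add to SAP 4.1.2 and 4.2.7.2.1 a pre-specified category *reinfection*: post-treatment viraemia with a chart-documented genotype, or known genotype 1 subtype, that differs from a known, non-mixed baseline type.
- Label as *undetermined* any positive without typing, and any positive in a patient whose baseline subtype was mixed or unknown.
- Report relapse12, relapse24 and relapse_late with and without the reinfection cases.
- List each patient with viraemia after EoT, with its timing, the available typing and any investigator assessment.
- Add chart-available post-treatment genotype and subtype to the data documented under the protocol, with no added testing. Protocol 9.6.1 limits the eCRF to protocol-specified data, so this needs a short protocol clarification as well as the SAP text.

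The cost is the wording and about one query per viraemic patient. The remaining weakness is that reinfection with the same subtype still counts as relapse, and the report should say so.
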